9.7 Patient-reported outcomes

The Functional Assessment of Cancer Therapy – Leukemia (FACT-Leu) and the 5-level EQ-5D version (EQ-5D-5L) will be collected and assessed.

In order to summarize patient-reported outcome (PRO) variables, assessments will be time slotted using time-windows as defined in study protocol. The baseline assessment is defined according to the rule for efficacy variables ([Section 3.5.1](#)).

The FAS will be used for all PRO summaries.

Frequency tables for compliance to completing all patient-reported questionnaires will be provided by treatment group and time point for FACT-Leu and EQ-5D-5L (Yes, fully completed/ Yes, partially completed/ No, patient missed scheduled assessment visit/ No, patient refused due to poor health/ No, patient refused (unrelated to health)/ No, study staff felt patient was too ill/ No, questionnaire not available in the appropriate language/ No, institutional error/

No, other). The number of patients with at least one post-baseline value of the respective questionnaire will be used as the denominator for frequency tables.

Descriptive statistics (mean, standard deviation, median, minimum, and maximum) will be used to summarize the scored scales at each scheduled assessment time point for the FACTLeu and EQ5D-5L (VAS) by treatment arm. Additionally, change from baseline in the scores at the time of each assessment will be summarized. Patients with an evaluable baseline score and at least one evaluable post baseline score during the treatment period will be included in the change from baseline analyses.

9.7.1 FACT-Leu

Assessment schedule

The questionnaire was to be completed at:

- Screening
- Induction phase : Cycle 1 Day 1 (C1D1), Cycle 2 Day 1 (C2D1) and end of induction phase
- Consolidation phase: prior to each consolidation cycle.
- Post-consolidation phase: Day 1 of each cycle and at end of post-consolidation phase
- Follow-up phase. Every 6 months.

Data derivation

For each subscales in [Table 9-4](#) Scoring will be done according to the instructions of the authors ([Cella 1997](#)). Higher score values for Physical well-being (PWB), Emotional well-being (EWB) and Additional Concerns (AC) indicate greater symptomatology or problems whereas higher scores for Social/family well-being (SWB) and Functional well-being (FWB) indicate lower symptomatology or problems.

Table 9-4 Fact-Leu scales

(Sub)Scale	Item numbers	Score range
Physical well-being (PWB)	GP1 to GP7	0 – 28
Social/family well-being (SWB)	GS1 to GS7	0 – 28
Emotional well-being (EWB)	GE1 to GE6	0 – 24
Functional well-being (FWB)	GF1 to GF7	0 – 28
Additional Concerns (AC)	BRM3, P2, BRM2, ES3, LEU1, TH1, TH2, HI12, BMT6, C2, C6, An7, N3, LEU5, LEU6, BRM9 and LEU7	0 – 68

Analyses

- For each treatment group, calculated scores and changes from baseline will be summarized by time window.
- The change from baseline will be evaluated in the calculated subscale scores using a mixed models for repeated measures (MMRM) up to end of post-consolidation phase. The following factors and covariates are included in the repeated measurement model: time, treatment, treatment by time interaction, age (<60/≥60 years) and baseline score.

Estimates for differences between treatments and 95% CI will be provided by time point. The test for treatment differences based on the MMRM will be provided. The use of this test will depend on the amount and type of missing data. Potential bias might be assessed by the following sensitivity analyses which will be carried out:

- Missing data will be imputed by the worst value observed for Midostaurin arm and the best for Placebo arm (high score = high level of quality of life) at the respective time window
- Missing data will be imputed by the mean of all non-missing values observed at the respective time window.

A plot will be prepared for the change from baseline score by time point and treatment group based on the repeated measurement model.

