10.5.5 Patient-reported outcomes

Responses to the FACT-Leu and EQ5D-5L, will be generated in accordance with the respective scoring manual.

A table of decomposition of patients will be created at each visit depicting the ‘number of patients in the analyses’, ‘patients died’, ‘patients achieved CR/CRi’, ‘patient refused data due to poor health’, ‘patient refused (unrelated to health)’, ‘study staff felt patient was too ill’, ‘patient missed appointment’, ‘other reasons’).

Descriptive statistics (mean, standard deviation, median, minimum, and maximum) will be used to summarize the scored scales at each scheduled assessment time point for the FACT-Leu and EQ5D-5L (VAS) by treatment arm. Additionally, change from baseline in the scores at the time of each assessment will be summarized. Patients with an evaluable baseline score and at least one evaluable post baseline score during the treatment period will be included in the change from baseline analyses.

Mixed models for repeated measures (MMRM) will be used to estimate the treatment effect on the FACT-Leu scores over time. MMRM are commonly used to analyze longitudinal data from randomized trials under the missing-at-random (MAR) assumption. The MMRM will

[REDACTED]

[REDACTED]

[REDACTED]

[REDACTED]

[REDACTED]

[REDACTED]

[REDACTED]

[REDACTED]

[REDACTED]

[REDACTED]

[REDACTED]

[REDACTED]

[REDACTED]

[REDACTED]

[REDACTED]

[REDACTED]

[REDACTED]

[REDACTED]

planned number of events, the futility boundary will need to be re-calculated (or updated) based on the actual number of observed events. Therefore, the observed p-value (or Z-test statistic) at the first interim analysis will be compared with the updated futility boundary.

A Haybittle-Peto stopping boundary will be used for efficacy interim and final EFS analyses (Peto et al 1976). At the second interim analysis, the observed p-value has to be less than $p=0.0001$ (i.e. $HR<0.601$) in order to conclude superior efficacy. If the study continues, the final analysis will be performed when approximately 285 EFS events have been documented or 5 years after the end of the study treatment for the last patient whichever occurs first. The final analysis criteria will be determined based on the actual number of events observed such that the overall significance level across all analyses is maintained at 0.025. It is estimated the the observed HR needs to be less than 0.80 to declare statistical significance at the final EFS analysis.

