6.8 Dose reductions, interruptions or permanent discontinuations

‘Dose changed’, ‘Dose interrupted’, and ‘Dose permanently discontinued’ fields from the exposure eCRF pages will be used to determine the dose reductions, dose interruptions, and permanent discontinuations, respectively.

The corresponding fields ‘Reason for dose change/dose interrupted’ and ‘Reason for permanent discontinuation’ will be used to summarize the reasons.

A dose change is either ‘change in prescribed dose level’ or ‘dosing error’ where actual dose administered is different from the prescribed dose.

For the purpose of summarizing interruptions and reasons, in case multiple entries for interruption that are entered on consecutive days with different reasons will be counted as separate interruptions. However, if the reason is the same in this block of entries, then it will be counted as one interruption.

Reduction: A dose reduction is, where the prescribed dose level is lower than the previous prescribed dose level or where the actual dose administered is lower than the calculated dose amount based on the prescribed dose. Therefore any dose change to correct a dosing error will not be considered a dose reduction. Only dose change is collected in the CRF, number of reductions will be derived programmatically based on the change and the direction of the change. In addition, if a patient moves to a less frequent regimen, such changes will then be counted as dose reductions.

7 Analysis of the primary objective

The primary objective of this study was to determine if the addition of midostaurin to standard induction and consolidation therapy, followed by single agent post-consolidation therapy improves event-free survival (EFS) in patients with newly diagnosed FLT3-WT AML.

As the study concluded at the first efficacy interim analysis due to futility, the endpoints will be derived and summarized based on the final data, but no testing (p-values) will be provided in the final CSR.

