8.2 Statistical hypothesis, model, and method of analysis

Assuming proportional hazards model for OS, the following statistical hypothesis for OS will be tested using a stratified log-rank test (stratified according to randomization stratification factor of age) at the one-sided 2.5% level of significance:

$$H02: \theta2 \geq 1 \text{ vs. } Ha2: \theta2 < 1$$

Where $\theta2$ is the hazard ratio (Midostaurin treatment arm vs. placebo arm) of OS.

The analyses for OS will be based on the FAS population according to the treatment group patients were randomized and the strata they were assigned at randomization. For the final CSR, OS will be summarized only descriptively. No testing will be performed. For the original testing plan, please refer to study protocol. OS will be estimated using the Kaplan-Meier method. The median OS along with 95% confidence intervals will be presented by treatment group. The stratified Cox regression will be used to estimate the HR of OS, along with 95% confidence interval. All OS analyses will be based on the FAS.

OS will be summarized between the 2 treatment groups within each of the subgroups as defined in [Section 3.8.5](#).

HRs and 2-sided 95% CIs will be provided based on the stratified Cox proportional hazards model. This model will use the BY statement to derive estimates by subgroup. Point estimates of HR and 2-sided 95% CI will be provided by subgroup in a forest plot.

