8.3 Analysis of secondary endpoints

The secondary efficacy variables include CR or CRi with adequate blood count recovery rate, MRD, DFS, CIR and CID. The assessment of these endpoints, except MRD, will be based on the IWG criteria for AML [[Cheson et al 2003](#), [ELN 2017 / Döhner et al 2017](#)] as per investigator assessment. All these endpoints will only be descriptively summarized with 95% CIs but without any p-values.

The rate of CR/CRi with adequate blood count recovery will be analyzed based on the FAS. However, DFS, Cumulative Incidence of Relapse (CIR) and Cumulative Incidence of Death (CID) will be analyzed based on data from responders (CR or CRi with adequate blood count recovery within 93 days after start of treatment) in the FAS. Assessment of relapse from CR or CRi with adequate blood count recovery, DFS, CIR and CID will not consider whether a patient received HSCT. All secondary analyses will include all data observed up-to the cut-off date, unless otherwise specified.

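### SAP 9.7.1 gives opposite score directions for three of five FACT-Leu subscales, so the worst-for-midostaurin imputation can run backwards; the compliance denominator also keeps patients who are not due

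*SAP*

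**What the plan says.** **Direction.** The data derivation part of SAP 9.7.1 says "Higher score values for Physical well-being (PWB), Emotional well-being (EWB) and Additional Concerns (AC) indicate greater symptomatology or problems". It gives the opposite direction for social/family (SWB) and functional well-being (FWB). Table 9-4 lists these five subscales with their ranges and no total score. The repeated-measures model (MMRM) is run on change from baseline in the subscale scores.

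**Sensitivity analyses.** There are two. The first replaces missing values by "the worst value observed for Midostaurin arm and the best for Placebo arm (high score = high level of quality of life"; the parenthesis closes there and excepts no subscale. The second is direction-neutral: "Missing data will be imputed by the mean of all non-missing values observed at the respective time window".

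**Scoring source.** The SAP refers to the questionnaire authors' instructions. Protocol 10.5.5 says that responses "will be generated in accordance with the respective scoring manual". Neither document reproduces the instructions or lists reversed items.

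**Testing.** For FACT-Leu, "The test for treatment differences based on the MMRM will be provided", with its use made to depend on how much data is missing and of what type. Elsewhere tests are dropped: for EFS, "but no testing (p-values) will be provided in the final CSR" (SAP 7); for OS, "No testing will be performed" (SAP 8.2); for the secondary efficacy endpoints, "All these endpoints will only be descriptively summarized with 95% CIs but without any p-values" (SAP 8.3).

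**Compliance.** SAP 9.7 tabulates questionnaire completion by arm and time point in nine categories, none of which is death or not due. The denominator is the same at every time point: patients with at least one post-baseline value.

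**The concern.** The two direction statements sit in one section and apply to the same scores, so they cannot both hold for PWB, EWB and AC. Either way something needs correcting:

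- If the derivation sentence is right and the parenthesis is programmed as written, missing midostaurin values receive the best observed score and missing placebo values the worst. A check meant to count against midostaurin then counts for it.
- If scoring makes high values good throughout, the imputation is right. The SAP then tells readers to interpret three subscales the wrong way round, including their MMRM treatment differences.

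FACT-Leu keeps a treatment test that EFS, OS and the listed secondary efficacy endpoints have lost. Of its two sensitivity analyses, only the worst/best one stresses the result against midostaurin. SAP Section 1 records that decisions on the final analysis were taken after unblinding, so the direction should be fixed in writing and not left to programming.

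The compliance tables raise a related problem. Whether the test is used depends on missing data, but a rate that counts patients who were never due does not show how much is missing.

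**Working it through.** **1. Table 9-4 ranges.** Items are scored 0–4 (Protocol Appendix 2). PWB, SWB and FWB: 7 × 4 = 28. EWB: 6 × 4 = 24. AC: 17 × 4 = 68. All five ranges reproduce, but they are the same in either direction and so do not settle it.

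The printed items do not settle it either. With no reversal, a patient in the worst health scores 28 on PWB and one in the best health 0. The corresponding EWB scores are 20 and 4, and the AC scores 60 and 8, because GE2 (in EWB) and C6 and An7 (in AC) are worded positively. EWB and AC therefore need some items reversed to use their full stated range in either direction.

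**2. The two statements side by side.**

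| Subscale | Derivation sentence | Imputation rule | Agree |
|---|---|---|---|
| PWB | high = worse | high = better | no |
| EWB | high = worse | high = better | no |
| AC | high = worse | high = better | no |
| SWB | high = better | high = better | yes |
| FWB | high = better | high = better | yes |

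**3. Gap between the two readings.** Let pM and pP be the missing shares in the midostaurin and placebo arms, and RM and RP the observed ranges (highest minus lowest). Under high = good, missing midostaurin values get the low and missing placebo values the high. Under high = problems, the reverse. Observed and baseline values are identical in both, so they cancel from the difference in arm means (midostaurin minus placebo):

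gap = pM × RM + pP × RP

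The documents give no missing shares or observed ranges, so these inputs are assumed.

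| Assumed missing (M / P) and range | PWB | EWB | AC |
|---|---|---|---|
| 10% / 10%, half scale | 0.2 × 14 = 2.8 | 0.2 × 12 = 2.4 | 0.2 × 34 = 6.8 |
| 20% / 20%, full scale | 0.4 × 28 = 11.2 | 0.4 × 24 = 9.6 | 0.4 × 68 = 27.2 |
| 30% / 10%, full scale | 0.4 × 28 = 11.2 | 0.4 × 24 = 9.6 | 0.4 × 68 = 27.2 |

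With equal shares p, equal ranges R and no true difference, each reading moves the difference by p × R. For PWB at 20% and full range that is 0.2 × 28 = 5.6: if high means worse, an intended shift of +5.6 becomes −5.6.

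A simulation of PWB (assumed mean 10, SD 6, 100 per arm, no true difference, high = worse) agrees. At 10, 20 and 40% missing, the intended shifts were +2.53, +5.08 and +10.03, and the backwards shifts −2.61, −5.20 and −9.95.

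**4. Compliance.** Under Protocol 4.2.1, patients in remission after induction 1 go straight to four consolidation cycles, so they are not due at induction cycle 2 day 1. Patients in remission only after induction 2 receive three consolidation cycles, so they are not due before cycle 4. Let N be the fixed denominator, a the forms completed at induction cycle 2 day 1 and b those completed before consolidation cycle 4. The two groups do not overlap, so a/N + b/N ≤ 1, and the smaller rate is at most 50% even if every due form is returned.

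Examples with assumed counts:

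- N = 80, of whom 32 receive induction 2 and all return forms: the SAP rate is 32/80 = 40%, the due-based rate 100%. Consolidation cycle 4 can then reach at most 48/80 = 60%.
- Late visit, 24 due and 19 complete: SAP rate 19/80 = 24%, due-based rate 19/24 = 79%.
- Early visit, 64 complete, all 80 due, plus 20 randomised patients who never return a post-baseline form: SAP rate 64/80 = 80%. The due-based rate is 64/100 = 64% if all 20 were due, 64/90 = 71% if 10 were, and 80% if none were.

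The bias can therefore go either way.

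**The case against.** The operative words of the rule are worst and best, and the parenthesis is only a gloss. A programmer who follows each subscale's own direction would impute correctly, and if scoring makes high values good throughout, the rule is right as it stands. Scoring detail may also lie in the authors' instructions, in the appendices that SAP Section 12 leaves to a prior SAP, or in the redacted protocol text on the MMRM. This stands as a limit: the documents show that the rule can run backwards, not that it did. It does not remove the contradiction in SAP 9.7.1.

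The sizes rest on assumed inputs, and the gap between readings is twice the one-way shift when shares and ranges are equal. That is also fair, and both figures are given above. What is affected is one sensitivity analysis of a secondary patient-reported outcome in a trial already stopped for futility.

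On compliance, the Protocol 10.5.5 per-visit table does list deaths, SAP 4.5 reports numbers entering each phase, and the denominator can be read as data availability among responders. These soften the point. None of them gives a rate among patients due, and no listed category separates a patient not due from one who missed a form. One sentence in Protocol 4.2.2 pairs one or two inductions with 3 or 4 consolidation cycles respectively, the reverse of Protocol 4.2.1, 6.1.1.1, 6.1.5 and 7.1.3, and the passages should be reconciled. On that reading the 100% bound would not hold, but the induction cycle 2 problem would.

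**Conclusion.** The concern holds. SAP 9.7.1 contradicts itself on PWB, EWB and AC, and nothing in the available text resolves it. Read literally, the only sensitivity analysis designed to count against midostaurin favours it on three of five subscales. Under the assumed 10–20% missing per arm and half to full observed range, the two readings differ by 2.8 to 11.2 points on PWB, 2.4 to 9.6 on EWB and 6.8 to 27.2 on AC. These are illustrations, not bounds. Confidence in the contradiction is high; which sentence is wrong cannot be decided from these documents.

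The fixed compliance denominator is a second, lesser fault. It needs no assumed counts to show that at least one of two scheduled visits must report 50% or less.

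**What to change.** - State one direction for each subscale after scoring under the cited instructions, name the reversed items (GE2, C6 and An7 are worded against the rest of their scales), and correct whichever sentence disagrees.
- Define worst and best for the imputation by that direction, subscale by subscale, and check the scoring and imputation programs against it.
- At each time point, use as compliance denominator the FAS patients alive and due for the questionnaire. Tabulate those not due by reason: died; relapsed or left the schedule; visit not applicable (no induction 2, or no consolidation cycle 4). The Protocol 10.5.5 table covers only the first, so the others must be added.

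The cost is SAP wording and a check of the scoring, imputation and compliance programs, with no new data. Reported compliance will rise where patients not due are removed and may fall where patients who never returned a form were due.

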This statistical analysis plan (SAP) describes all planned analyses for the clinical study report (CSR) of study CPKC412E2301: a phase III, randomized, double-blind clinical trial of chemotherapy with daunorubicin or idarubicin and cytarabine for induction and intermediate dose cytarabine for consolidation plus midostaurin (PKC412) or placebo in newly diagnosed patients with FLT3-MN (SR<0.05) AML (FLT3 mutant to wild type signal ratio below the 0.05 clinical cut-off).

The content of this SAP is based on protocol CPKC412E2301 amendment 1. All decisions regarding final analysis, have been made prior to final database lock but after unblinding of the study data.

The first interim analysis of the primary endpoint (Event Free Survival (EFS)) for futility has been performed and the study was stopped due to lack of efficacy on 23-Sep-2019 based on DMC recommendation. Subsequently, investigators were notified on the futility outcome and study was unblinded not only for Novartis but also the investigators. While majority of patients discontinued from the study within subsequent weeks, some patients decided to continue protocol planned study treatment. This SAP now describes the analyses for the final CSR which will be generated when all patients discontinued study treatment.

The originally planned efficacy and safety analyses are reduced based on the futility outcome. However, some subgroup analyses have been added (e.g. safety and efficacy by anthracyclin for AML induction therapy (Daunorubicin vs Idarubicin)) and some analyses are only performed now for the final CSR (e.g. QoL, PK, [REDACTED]).

2 Study design, objectives and endpoints

[figure not shown]
This is a randomized, double-blind, multi-center, placebo-controlled phase III study using a group sequential design with two interim analyses for the primary endpoint event-free survival (EFS) and regular safety looks. The study population comprises 502 adult patients with newly diagnosed FLT3-MN (SR<0.05) AML. Patients will be stratified according to age (<60 vs. ≥ 60 years) and will be randomized in a 1:1 ratio into one of two treatment arms:

- Midostaurin + chemotherapy

Or

- Placebo + chemotherapy

Figure 2-1 Study design

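### The SAP drops p-values for EFS, OS and the listed secondary efficacy endpoints after the futility stop, yet keeps an undefined MMRM test on five FACT-Leu subscales with no alpha, lead scale or exploratory label

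*SAP*

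**What the plan says.** The opening of SAP Section 7 says that, because the study ended at the first interim analysis, the primary endpoint will be summarised "but no testing (p-values) will be provided in the final CSR". Section 8.2 makes OS descriptive in the final report, without a test. Section 8.3 lists CR/CRi rate, MRD, DFS, CIR and CID and says: "All these endpoints will only be descriptively summarized with 95% CIs but without any p-values".

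Section 9.7.1 differs. For FACT-Leu, "The change from baseline will be evaluated in the calculated subscale scores" by "mixed models for repeated measures (MMRM) up to end of post-consolidation phase". Table 9-4 has five scales: physical, social/family, emotional and functional well-being, and additional concerns. The model contains time, treatment, their interaction, age group and baseline score. Two kinds of output follow. The first is estimation: "Estimates for differences between treatments and 95% CI will be provided by time point". The second is inference: "The test for treatment differences based on the MMRM will be provided", qualified by "The use of this test will depend on the amount and type of missing data". Two imputation-based sensitivity analyses are then described.

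The Introduction to the SAP says that decisions on the final analysis "have been made prior to final database lock but after unblinding of the study data". It also names quality of life among the analyses done only now, for the final report.

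**The concern.** The SAP takes a clear position after the futility stop: estimates and intervals, no p-values. The FACT-Leu test departs from it without a reason. Protocol Section 10.5 lists health-related quality of life alongside the other secondary efficacy objectives, so nothing obvious sets it apart.

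The test is also not specified well enough to be run in only one way. With a treatment-by-time interaction in the model, it could mean the treatment main effect, the interaction, or a contrast at a visit. No subscale leads, and no significance level is given.

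The condition on missing data adds discretion. No amount or pattern of missingness is named that would switch the test on or off, and the decision would be taken by people who can see treatment assignment. The condition is likely to matter: the Introduction reports that investigators were unblinded too and that most patients left the study within weeks of the futility notice.

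At stake is a nominally significant subscale being read as a quality-of-life effect in the report of a trial that stopped for lack of efficacy.

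**Working it through.** The documents give no alpha, power or error rate for FACT-Leu, so there is no planned figure to reproduce.

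**Inputs**
- Number of subscales: 5 (SAP Table 9-4).
- Tests per subscale: 1. Section 9.7.1 speaks of the test in the singular and attaches only estimates and intervals to time points.
- Significance level: not stated. Assumed two-sided 5% (critical value 1.96), to match the 95% confidence intervals.
- Correlation between the subscale test statistics: not in the documents. Assumed common to all pairs and varied.

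**Independent subscales**

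P(at least one p < 0.05 under no effect) = 1 − (1 − 0.05)^5 = 1 − 0.774 = 0.226.

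**Correlated subscales**

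Simulation of five equally correlated standard normal statistics under no effect, counting runs in which any exceeds 1.96 in absolute value:

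| Correlation | P(at least one of five) |
|---|---|
| 0 | 0.23 |
| 0.3 | 0.21 |
| 0.5 | 0.18 |
| 0.7 | 0.15 |
| 0.8 | 0.13 |

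At correlation 0.5 the unrounded value is 0.184, and 0.184 / 0.05 = 3.7 times the nominal level. Counting only results in midostaurin's favour, the rate at that correlation is 0.092 against 0.025, again 3.7 times. The expected number of false positives is 5 × 0.05 = 0.25 at any correlation.

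**Side by side**

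| Endpoint | SAP section | P-value in the final report |
|---|---|---|
| EFS | 7 | No |
| OS | 8.2 | No |
| CR/CRi, MRD, DFS, CIR, CID | 8.3 | No |
| FACT-Leu subscales (five) | 9.7.1 | Yes, subject to an undefined missing-data condition |

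**The case against.** The strongest reply is that no error-controlled claim is at stake. The hierarchy in Protocol Section 10.5.1 covers EFS and OS only, and it was never opened. Multiplicity control is not normally demanded of a non-key patient-reported outcome in a stopped trial. The no-p-value sentence in SAP Section 8.3 covers the endpoints it lists and does not name patient-reported outcomes, so Section 9.7.1 does not strictly contradict it. Making the test depend on missing data can be read as caution, and the sensitivity analyses address possible bias. All of this stands, and it limits the point to reporting. It does not explain the exception, define the test, or say what missingness would decide its use.

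Three stronger readings are tempting, and the documents do not support them.
- A reader might multiply five subscales by the up to 19 scheduled post-baseline time points (1 + 1 + 4 + 12 + 1) and call a chance finding likely. Section 9.7.1 promises only estimates and intervals by time point. Those intervals serve the protocol's endpoint, which is change from baseline at each time point, and they would remain after the fix. No patient could supply more than 18 of the 19, because a second induction cycle means three consolidation cycles rather than four.
- A reader might infer that these are the only treatment-effect tests left in the report. Material between SAP Sections 9.7.1 and 9.13 is blacked out, so this cannot be verified.
- A reader might infer that the test was added after results were seen. Protocol Section 10.5.5 already planned an MMRM to estimate the treatment effect, and a first SAP version is dated 02-Sep-2019, before the stop on 23-Sep-2019. That version is not available, so the origin of the test wording is unknown. The protocol text also breaks off where it begins to describe the model, so a rule there cannot be excluded, although SAP Section 9.7.1 reads as complete.

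**Conclusion.** The point holds as a reporting inconsistency with a modest, quantifiable risk. An unexplained, undefined and conditionally used test remains on five subscales beside efficacy endpoints whose p-values were removed. The chance of at least one false positive is 0.18 in the central case and 0.13 to 0.23 over correlations from 0.8 to 0. This rests on one overall test per subscale, a two-sided 5% level and equal correlation, all of which are assumptions because the SAP does not settle them. A chance finding is therefore several times the nominal rate but not probable. The trial's type I error control is intact; what suffers is the interpretation of a nominal p-value in the final report.

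**What to change.** In the analysis part of SAP Section 9.7.1, delete the sentence that provides the test and the next one, which makes its use depend on missing data. Put in their place: *MMRM treatment differences will be presented with 95% CIs descriptively; no p-values will be provided, consistent with Sections 7, 8.2 and 8.3, and all FACT-Leu results are exploratory.*

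The model, the by-visit estimates, the plot and the sensitivity analyses stay as they are. Do not add a newly chosen lead scale or summary contrast: naming one after unblinding would introduce the kind of post hoc choice that the change is meant to remove.

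The cost is a wording change. The only loss is that the report shows no p-values for individual subscales.

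### The FACT-Leu mean-imputation sensitivity analysis returns an answer set by the missing fraction, so it cannot test the robustness of the MMRM

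*SAP*

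**What the plan says.** The main FACT-Leu analysis in SAP 9.7.1 is an MMRM on change from baseline in each subscale, with terms "time, treatment, treatment by time interaction, age (<60/≥60 years) and baseline score". Its output is stated as "Estimates for differences between treatments and 95% CI will be provided by time point". Protocol 10.5.5 describes such models as operating "under the missing-at-random (MAR) assumption"; the text that follows is blacked out.

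On missing data, SAP 9.7.1 first says of the MMRM test: "The use of this test will depend on the amount and type of missing data". It then adds "Potential bias might be assessed by the following sensitivity analyses which will be carried out" and lists two rules:

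- "Missing data will be imputed by the worst value observed for Midostaurin arm and the best for Placebo arm"
- "Missing data will be imputed by the mean of all non-missing values observed at the respective time window"

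The first rule names each arm. The second names neither and refers to all values, so pooling is the natural reading, though it is not stated outright. No multiple imputation or variance correction is given, and nothing says which missing visits are to be filled. SAP 9.7 restricts change-from-baseline analyses to patients with an evaluable baseline score and at least one evaluable later score on treatment. Neither document gives a missing fraction, SD, effect size or power for FACT-Leu.

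**The concern.** Filling with a single mean gives every missing patient the same value and then counts the fills as observations. If one mean serves both arms, the two arms are pulled together by an amount that depends only on how much is missing, not on why.

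Missing data are likely to be substantial. The SAP Introduction says most patients left within weeks of the futility stop. Induction failures stop treatment and move to survival follow-up, and Protocol 7.1.8 lists no questionnaires there; Protocol 7.1.7 lists them only for efficacy follow-up.

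The risk is to how the clinical study report is read. A small, precise-looking difference beside the MMRM result could be taken as evidence that missing scores hide neither benefit nor harm. It would be no such evidence.

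**Working it through.** The plan has no figure of its own on this point to reproduce.

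**1. Effect on the difference (pooled mean).** Let mT and mC be the missing fractions in the midostaurin and placebo arms, d the observed difference in means, and wT midostaurin's share of the observed scores. The pooled mean is the placebo mean plus wT·d. Substituting it for the missing scores in both arms gives

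filled difference = d × [(1 − mT) + (mT − mC)·wT].

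- Equal missingness: the factor is 1 − m, so 0.90, 0.70, 0.50 and 0.40 at 10%, 30%, 50% and 60%.
- 20% v 40% missing, equal arms: wT = 0.80/1.40 = 0.571; factor 0.80 − 0.20 × 0.571 = 0.686.
- 46% v 59% missing: wT = 0.54/0.95 = 0.568; factor 0.54 − 0.13 × 0.568 = 0.466.

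For unadjusted means this is algebra and holds for any missingness mechanism.

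**2. Effect on the SE.** With n per arm, common SD s and equal m, the observed-data SE is s√(2/[n(1 − m)]). After filling, the within-arm variance is about (1 − m)s² and the apparent sample size is n, so the SE is s√(2(1 − m)/n), which is (1 − m) times the observed-data SE. At n = 251, s = 1 and m = 0.5: 0.126 becomes 0.063.

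**3. Simulation.** Assumptions: standardised scores; 251 per arm (502/2, the planned size); missing completely at random; baseline correlation 0.5; true difference 0.3 SD, or 0 for false positives; ANCOVA at one visit; 3,000 runs per scenario.

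| Missing | Observed data: estimate (SE) | Pooled fill: estimate (SE) | Width ratio | Coverage of 0.3 | False positives, pooled | False positives, by arm |
|---|---|---|---|---|---|---|
| 10% | 0.302 (0.0816) | 0.272 (0.0747) | 0.92 | 93% | 4.3% | 7.4% |
| 30% | 0.297 (0.0925) | 0.209 (0.0681) | 0.74 | 72% | 5.0% | 17.6% |
| 50% | 0.296 (0.1097) | 0.148 (0.0593) | 0.54 | 26% | 5.9% | 32.7% |
| 60% | 0.301 (0.1227) | 0.120 (0.0539) | 0.44 | 9% | 4.9% | 44.9% |

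Hand check at 50%: (0.300 − 0.148)/0.0593 = 2.56, and Φ(1.96 − 2.56) = Φ(−0.60) = 0.27, against 26% simulated. The coverage loss comes mainly from where the interval is centred.

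**4. Against a mixed model.** Four visits with monotone dropout, 800 runs. A mixed model valid under missing at random gave 0.300, 0.300, 0.298 and 0.297 (SE 0.082, 0.092, 0.106, 0.117) at 10%, 30%, 50% and 60% missing. The pooled fill gave 0.270, 0.209, 0.148 and 0.118 (SE 0.075, 0.068, 0.059, 0.054).

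**5. Mean by arm.** The estimate stays at about 0.30. The reported SE at 50% missing is 0.059, while the estimator's actual sampling SD under no effect is 0.118.

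**6. How much might be missing late?** This is an illustration only, assuming an EFS event ends questionnaire completion. Planned treatment is 17 cycles × 28 days = 476 days, or 15.6 months (Protocol 6.1.5). With the design's 12-month control median, 0.5^(15.64/12) = 0.405 remain event-free, so about 60% are missing. At HR 0.675, 0.405^0.675 = 0.543, so about 46%.

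**The case against.** Most of the case on the other side limits the point rather than removing it.

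- **Pooling is not stated.** True. Under arm-specific filling the shrinkage disappears, but a worse inferential fault replaces it (step 5). Neither reading gives a usable analysis.
- **The pooled SE is not wrong for what it estimates.** This stands. A reader might infer intervals that are far too narrow and too many false positives. Under the pooled reading the reported SE matches the estimator's sampling SD (0.0590 v 0.0605 at 50% missing, no effect). False positives stay between 4.3% and 6.0% across the pooled scenarios, and power falls rather than rises (0.61 v 0.73 for the mixed model at 60%). Understated variance belongs to the arm-specific reading only.
- **The size depends on an unstated missing fraction.** This stands. At 10% missing the effect is slight.
- **Not everyone is filled.** A reader might infer that all patients who died or left are imputed. The restriction in SAP 9.7 excludes those without a baseline and a later score. It does not exclude deaths and dropouts after the first later score.
- **Reference-based imputation also attenuates.** This stands, so attenuation alone is not the error. The difference is that it states an assumption about the unseen scores and carries imputation uncertainty into the interval.
- **The MMRM test.** A reader might infer that keeping it contradicts "no testing (p-values) will be provided in the final CSR". That statement is in SAP Section 7 on the primary objective; SAP 8.2 and 8.3 say the same for OS and the listed efficacy secondaries. None names patient-reported outcomes, so there is no contradiction. Nor can a test count be derived, because the SAP ties differences and intervals to time points but not the test.
- **Context.** The main analysis is the MMRM, completion is tabulated by reason, and the trial had stopped for futility. This stands and limits the importance.

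**Conclusion.** The point holds as a fault in one planned secondary sensitivity analysis. On the natural reading, the mean fill returns the observed difference times a known factor, with an interval about that much narrower. It therefore adds no information about the missing scores and can neither support nor challenge the MMRM. The factor is algebra: 1 − m for equal missingness, and otherwise between the two arms' observed fractions. Coverage of about 93%, 72%, 26% and 9% rests on the assumed 0.3 SD effect, 251 per arm, baseline correlation 0.5 and data missing completely at random. A larger true effect would worsen it. The smaller sample to be expected after the stop would soften it. Missingness related to health would add bias to every method shown. The main fault is bias toward no difference, and no efficacy conclusion depends on it.

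**What to change.** In SAP 9.7.1, replace the mean fill with multiple imputation combined by Rubin's rules. Use either of:

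- delta adjustment over a stated range of deltas for each subscale; or
- a reference-based method with its assumption written out.

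Apply it within the change-from-baseline population of SAP 9.7, only to patients alive and due at the visit, and say how scores after death are handled. Because the study is already unblinded, set the deltas or reference assumption before the FACT-Leu comparison is run. The MMRM and its test can stay as they are.

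The cost is a few lines of SAP text, a standard imputation program and wider intervals. The results will be valid only under the stated delta or reference assumption, so the report should present them that way.
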